1.2.3 Randomisation

Eligible patients will be randomised (using randomisation ratio 1:1:1) to Olaparib monotherapy, AZD6738+Olaparib or AZD1775+Olaparib. Effective April 2019, eligible patients will be randomised (using randomisation ratio 1:1) to Olaparib monotherapy or AZD6738+Olaparib.

The randomisation scheme will be stratified based on:

- the primary patient population: stratum A (*BRCAm*), stratum B (non *BRCAm* HRR m), stratum C (non HRR m) as defined in Section 1.2.1
- and patient's prior platinum-based therapy (no / yes)

so that there will be a total of 6 strata: An, Ay, Bn, By, Cn, Cy.

The 3 primary patient populations A, B, C will be capped to have approximately 150 patients each (approximately 50 patients per treatment arm). It is expected that the non-HRR m patient population will be recruited fastest.

1.2.4 Diagnostic journey and study flow chart

Please refer to the diagnostic journey (Figure 1) and study flow chart (Figure 2).
(Randomization to AZD1775+Olaparib treatment arm closed in April 2019.)

Figure 1 Diagnostic journey

Note: Stratum A: *BRCAm*, stratum B: non *BRCAm* HRRm, stratum C: non HRRm. The AZD1775+Olaparib treatment arm was closed following the ISRC meeting on the 17 April 2019.

[figure not shown]
[figure not shown]

Figure 2 Study flow chart

In addition, a survival follow-up is conducted every 8 weeks (± 7 days) after the Safety Follow Up visit.

1.2.5 Study governance and oversight

AstraZeneca Unblinded Review Committee

An AstraZeneca Unblinded Review Committee (AZ URC) will be convened and will conduct a review of the planned interim efficacy analyses described in Section 5. Safety will also be reviewed at this time. Full details of the AZ URC procedures and processes can be found in the AZ URC Charter.

Independent Safety Review Committee

An independent Safety Review Committee (ISRC) will monitor safety and tolerability in the study at regular intervals. Full details of the ISRC procedures, processes and potential recommendations can be found in the ISRC Charter.

1.3 Number of events and patients

In the 3 primary patient populations A, B, C, for each of the 2 comparisons (AZD6738 + Olaparib vs Olaparib monotherapy, AZD1775 + Olaparib vs Olaparib monotherapy), 68 PFS events would have 80% power to show a statistically significant difference at the 2-sided 10% significance level if the assumed true treatment effects were hazard ratio (HR) 0.55. This translates to a 5 month benefit in median PFS over 6 months on Olaparib in the *BRCAm* patient population and a 4.17 month benefit in median PFS over 5 months on Olaparib in the non *BRCAm* *HRRm* patient population and in the non *HRRm* patient population if PFS is exponentially distributed.

Approximately 50 patients (450 patients overall) will be randomised to each of the 3 treatment arms within each of the 3 primary patient populations A, B, C so that data maturity for the PFS analysis is approximately 68%.

Following the decision of the ISRC to close recruitment to the AZD1775+olaparib arm in April 2019, fewer than 50 patients per strata will be randomised to this arm. The total number of patients randomised will be lower (approximately 350 patients overall). The study will only be sized to test for a difference between the AZD6738+olaparib vs. olaparib monotherapy arms.

Assuming 15 months non-linear recruitment, the required number of PFS events are expected to occur approximately 24 months after the first patient is randomised.

2. ANALYSIS SETS

2.1 Definition of analysis sets

2.1.1 Full analysis set

The full analysis set (FAS) will include all randomised patients with treatment arms assigned in accordance with the randomisation, regardless of the treatment actually received. Patients who were randomised but did not subsequently receive treatment are included in the FAS.

Patients randomized to the AZD1775+olaparib arm will be analysed as such, regardless of whether they discontinued study treatment entirely or received olaparib monotherapy after closure of the AZD1775+olaparib treatment arm in April 2019. The analysis of data using the FAS therefore follows the principles of intent to treat (ITT). All efficacy and CCI data will be summarised and analysed using the FAS. Disposition, demographic data, baseline characteristics, etc will be summarized using the FAS.

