1.4 Study Design

This is a prospective, open label, randomised, multi-centre Phase 2 study that will assess the efficacy and safety of olaparib monotherapy versus olaparib in combination with an inhibitor of ATR (ceralasertib) and olaparib monotherapy versus olaparib in combination with an inhibitor of WEE1 (AZD1775) in second or third line setting in patients with TNBC prospectively stratified by presence/absence of qualifying tumour mutation in genes involved in the HRR pathway. The study patient population will be stratified as described below:

- stratum A: patients with mutations in *BRCA1* or *BRCA2* (*BRCAm*)
- stratum B: patients with mutations in any of the following ^{CCI} genes involved in the HRR pathway (^{CCI} [REDACTED] and no mutation in *BRCA1* and no mutation in *BRCA2*
- stratum C: patients that have no detected tumour mutations in any of the ^{CCI} HRR genes mentioned above.

Following the ISRC meeting on 17 April 2019 a recommendation was made to close the AZD1775+olaparib treatment arm across all biomarker strata and that patients currently receiving treatment with AZD1775+olaparib treatment be offered the opportunity to continue olaparib monotherapy at the approved dose (300 mg bd). This recommendation was ratified by the AstraZeneca Unblinded Review Committee and implemented in protocol version 6.0. All patients randomized to this arm discontinued AZD1775 and continued on olaparib monotherapy increasing to the approved dose at the start of their next treatment ensuring a minimum 10 day wash out period from AZD1775 to olaparib 300 mg bd dosing to avoid DDI.

Within each stratum A, B and C, there will be further stratification by whether the patient received prior platinum-based therapy (yes/no).

The 3 treatment arms are:

Treatment Arm 1 – 300 mg bd olaparib continuous (28-day cycle)

Treatment Arm 2 – 160 mg od ceralasertib Days 1-7 + 300 mg bd olaparib continuous (28-day cycle)

Treatment Arm 3 – 150 mg bd AZD1775 Days 1-3 and 8-10 + 200 mg bd olaparib continuous (21-day cycle). This treatment arm was closed following the ISRC meeting on the 17 April 2019.

Due to the different schedules of administration of each of the treatment options as well as their different toxicity profiles, the study cannot be blinded. Given the open label design of

the study, efforts will be made to ensure robustness of the primary endpoint assessment and to avoid any unnecessary unblinding of the operational study team.

Two-stage consent process

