1.1.1 Primary objective

Patient Population	Primary Objective	Outcome Measure

 • BRCAm • Non BRCAm HRRm • Non HRRm 	To assess the efficacy of the combination of AZD6738+Olaparib and the combination of AZD1775+Olaparib compared with Olaparib monotherapy by assessment of progression-free survival (PFS)	
PFS using Blinded Independent Central Review (BICR) according to Response Evaluation Criteria In Solid Tumours (RECIST) 1.1
 
Sensitivity analysis of PFS using Investigator assessments according to RECIST 1.1

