4.1.8 General principles for statistical modelling and hypothesis testing

All statistical tests will be pairwise, i.e. comparing two treatment arms and there will be no “overall” tests of global null hypotheses (same distribution in all three treatment arms).

Any stratification in the statistical modelling will be based on the values entered into Interactive Voice Recognition System (IVRS) at randomisation, even if it is subsequently discovered that these values were incorrect. In case of at least 10% of mis-stratified patients (across all strata), a sensitivity analysis will be carried out using the (correct) baseline data collected in the eCRF.

Results of statistical analyses will be presented using 2-sided 90% CIs and 2-sided p-values for pairwise comparisons between

- AZD6738+Olaparib versus Olaparib monotherapy
- AZD1775+Olaparib versus Olaparib monotherapy
- and AZD6738+Olaparib versus AZD1775+Olaparib (as secondary analysis).

Two-sided p-values will be presented using 3 decimal places for all values ≥ 0.001 . The only categorical presentation to be used is when $p < 0.001$.

The types of statistical test(s) used to generate p-values or CIs, together with details of any stratification or prognostic factors, should be included in a footnote to the presentation or in

the text as appropriate. Any ‘post-hoc’ analyses (i.e., not pre-specified) will be clearly indicated on any outputs either by using the titles or footnotes as appropriate.

Primary statistical analyses comparing PFS based on BICR for each combination treatment arms to Olaparib will be conducted for the 3 patient populations *BRCAm*, Non *BRCAm* *HRRm* and Non *HRRm*.

Comparisons of PFS based on BICR for each of the combination treatment arms to Olaparib in the 2 patient populations *HRRm* and All will be conducted as secondary statistical analyses.

Secondary outcome measures will be analysed for the 3 patient populations *BRCAm*, Non *BRCAm* *HRRm* and Non *HRRm*, except

- ORR and OS, which will be analysed for all 5 patient populations
- Tumour and germline mutation status, which will be analysed only for the All patient population
- PK outcome measure $C_{\min,ssss}$, which will be analysed only for the All patient population

RECIST-based primary and secondary outcome measures based on Investigator assessments will also be analysed for sensitivity purposes.

Safety outcome measures and exploratory outcome measures will be analysed for the All patient population only, except

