4.2 Analysis Methods

4.2.1 Handling of multiplicity

Multiplicity adjustment will be considered within each of the 3 primary patient populations for PFS. The overall 2-sided alpha for each primary patient population will be 0.2, and a simple Bonferroni adjustment assigns 2-sided alpha of 0.1 to each of the 2 pairwise treatment arm comparisons to Olaparib monotherapy.

No further adjustments for multiplicity are planned, in particular no adjustments for interim analyses.

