4.2.10.8 Analysis of subject disposition and analysis sets

Summaries will include the number and percentage of patients by treatment arm:

- enrolled (informed consent received)
- randomised
- treated
- ongoing study treatment at the data cut-off (applicable for interim analyses)
- included in the FAS, SAF, or PK analysis set.

In addition, the number and percentage of patients who discontinued treatment and who discontinued the study, including a breakdown of the primary reason for discontinuation will be presented by treatment arm.

The number and percentage of patients randomized to AZD1775+olaparib who continue on olaparib monotherapy following the closure of the AZD1775+olaparib treatment arm in April 2019 will be presented.

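### PFS for AZD1775+olaparib keeps accruing after the April 2019 withdrawal of AZD1775, and no planned analysis isolates the period on the combination; a supplementary analysis cut at closure is a cheap improvement

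*SAP*

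**What the plan says.** The comparison is still a primary one. SAP 1.1.1 keeps AZD1775+olaparib versus olaparib on PFS in the primary objective. SAP 4.1.8 says: "Primary statistical analyses comparing PFS based on BICR for each combination treatment arms to Olaparib will be conducted" in the three biomarker populations, and adds ceralasertib+olaparib versus AZD1775+olaparib as a secondary comparison. SAP 4.2.1 still gives the AZD1775 comparison its share of alpha: "a simple Bonferroni adjustment assigns 2-sided alpha of 0.1 to each of the 2 pairwise treatment arm comparisons to Olaparib monotherapy".

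On the closure, SAP 2.1.1 says: "Patients randomized to the AZD1775+olaparib arm will be analysed as such, regardless of whether they discontinued study treatment entirely or received olaparib monotherapy after" April 2019, and describes this as following intention to treat. SAP 3.3.1 counts PFS events whatever happens to treatment.

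The documents differ on what happened to the patients:
- Protocol 1.4: "All patients randomized to this arm discontinued AZD1775 and continued on olaparib monotherapy increasing to the approved dose".
- Protocol Table 5 (footnote **): all discontinued AZD1775, and olaparib 300 mg bd was offered.
- SAP 1.2.2: patients continue olaparib alone or stop all study treatment.
- Protocol 6.8: after an earlier olaparib dose reduction, the investigator may raise the dose stepwise.

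Protocol 1.4, Protocol Table 5 and SAP 1.2.2 must be reconciled.

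The one output added for the switch is a disposition count of the patients "who continue on olaparib monotherapy following the closure of the AZD1775+olaparib treatment arm in April 2019 will be presented" (SAP 4.2.10.8).

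**The concern.** The objective asks about the combination. After April 2019 nobody in the arm was meant to receive it, and those who continued were offered the control drug. Follow-up in which little or no difference is expected is pooled with follow-up in which a difference could exist. One hazard ratio across both periods averages them, and a reader of the study report could not tell how much of a value near 1 comes from the drug and how much from the closure.

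This works in both directions. Protocol 1.2.2 says the arm was closed for increased toxicity and no suggestion of benefit, so dilution could mask harm as well as benefit.

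The planned sensitivity analyses do not separate the periods. The attrition analysis in SAP 4.2.5 censors at subsequent therapy, but olaparib alone is continued study treatment. The optional analysis in Protocol 8.5 selects by AZD1775 starting dose.

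**Working it through.** **Plan's own figure.** SAP 1.3: "68 PFS events would have 80% power to show a statistically significant difference at the 2-sided 10% significance level". The design effect there is HR 0.55. Schoenfeld with equal allocation: d = 4(1.645 + 0.842)² / (ln 0.55)² ≈ 69.2, so 70 events. With 68 events the power is Φ(|ln 0.55|·√68/2 − 1.645) = 79.4%. The plan's 68 events and 80% are reproduced within rounding.

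**Inputs from the documents.**
- Exponential PFS with olaparib median 6 months (BRCAm) or 5 months (the other two strata); HR 0.55 (SAP 1.3).
- Start in Q1 2018 (Protocol 9.3) and closure in April 2019, so about 12-15 months of accrual before closure.
- Events expected about 24 months after first randomisation, with 15 months of recruitment (SAP 1.3), so the data cut-off is taken as 24 − 15 = 9 months after closure.

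**Assumptions, because the documents give no figure.** Accrual to the arm is uniform or back-loaded over those 12 or 15 months. In the base case every event-free patient moves to the control hazard at closure.

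**Model.** AZD1775 arm hazard = HR × control hazard before closure, and = control hazard after it. One-covariate Cox estimate in large simulated samples (at least 200,000 per arm), over all combinations of accrual length, accrual shape and control median.

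At a true HR of 0.55, 60-79% of the arm is event-free at closure and 51-71% of its PFS events fall after it. Estimates:

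| True HR | Full follow-up (as planned) | Both arms cut at closure |
|---|---|---|
| 0.55 | 0.70-0.80 | about 0.55 |
| 0.70 | 0.80-0.87 | about 0.70 |
| 0.90 | about 0.93-0.96 | about 0.90 |
| 1.00 | about 1.00 | about 1.00 |
| 1.30 | 1.13-1.20 | about 1.30 |
| 1.50 | about 1.22-1.33 | about 1.50 |

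On the log scale, at a true HR of 0.55: 1 − ln 0.70/ln 0.55 = 1 − 0.357/0.598 = 40% of the effect is lost at the low end, and 1 − 0.223/0.598 = 63% at the high end.

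**Weaker version.** If 30% of event-free patients keep their pre-closure hazard, for example because they had already stopped AZD1775, 0.55 becomes about 0.65-0.72. If 50% do, it becomes about 0.62-0.67.

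**Precision.** About 350 patients in total, less about 300 in the two open arms, leaves about 50 in this arm, or 17 per stratum (derived, not stated). With 17 against 50 controls at 68% maturity there are 0.68 × 67 ≈ 46 events. Power = Φ(|ln HR|·√(d·p(1−p)) − 1.645) with p = 17/67, which gives 54% at HR 0.55, 28% at 0.70 and 16% at 0.80.

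**The case against.** The strongest reply is that the analysis is intention to treat, openly stated in the SAP. That stands. SAP 2.1.1 addresses the switch, covers both those who continued and those who stopped, and says how they are analysed. Events before closure still reflect the combination. A reader might infer that the hazard ratio no longer measures the combination, or that the full analysis set result is wrong and should be replaced. The documents do not support either: it is a legitimate treatment-policy estimate, and preferring the truncated one as the sole basis for conclusions would be a choice of estimand.

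A reader might also infer from Protocol 1.4 that every remaining patient was moved to the control regimen at the control dose. Protocol Table 5, SAP 1.2.2 and SAP 2.1.1 itself do not say that: olaparib was offered, stopping all study treatment was possible, and stepwise escalation was allowed. The change came at each patient's next cycle and stayed on a 21-day cycle. Patients who stopped everything need not have the control hazard, so even the direction of the shift is conditional.

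The size is contestable too. HR 0.55 is the design effect, while the arm was closed with no suggestion of benefit, and near 1 the dilution is small. Recruitment to the non-HRRm stratum was paused after the 75th patient, which lengthens pre-closure follow-up there; with a 2-month gap 0.55 becomes 0.67-0.76. Patients already off AZD1775 reduce the shift further.

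Finally, the study is now sized only for ceralasertib+olaparib versus olaparib (SAP 1.3), and the first unblinded review was to see investigator PFS and Week 8 non-progression in the non-HRRm stratum. That look covers one stratum and is not a pre-closure analysis for the study report. These points limit the consequence. They do not supply the missing estimate.

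**Conclusion.** This holds as a cheap improvement. A comparison that remains in the primary objective, with its own alpha, will be reported from follow-up that mixes time on the combination with time after its withdrawal, and no planned study-report analysis separates the two.

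The pull toward 1 depends on a true hazard ratio different from 1 and a post-closure hazard close to control. Its size rests on exponential PFS, the plan's medians, the assumed accrual pattern and a cut-off 9 months after closure. The documents do not give the number event-free in April 2019 or the number who took up olaparib, so the results are ranges; the 0.70-0.80 figure is a base case at the design effect and should not be read as a forecast. The conclusion on ceralasertib+olaparib versus olaparib is untouched.

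**What to change.** In SAP 4.2.5, for the two PFS comparisons that include AZD1775+olaparib, add a supplementary analysis:
- restricted to patients randomised up to closure;
- one administrative data cut-off at 17 April 2019 in both arms, with patients event-free then censored at their last evaluable RECIST assessment on or before that date;
- the same stratified log-rank test and Cox model, unstratified if events are too few.

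Keep the full analysis set result and label it as the effect of AZD1775+olaparib until closure, then olaparib or no study treatment. Report the two side by side and present the AZD1775 comparison as descriptive. Reconcile Protocol 1.4, Protocol Table 5 and SAP 1.2.2 on what patients received after closure.

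Do not extend the cut to expected duration of response: the stratified parametric fit in SAP 4.2.8.4 is not realistic with so few truncated responses. If ORR is also cut at closure, apply the interim denominator rule in SAP 3.4.1, so that patients randomised shortly before closure are not counted as non-responders by default.

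The cost is one SAP paragraph and a re-run of existing programs with an earlier cut-off. The price is fewer events and a wider confidence interval. The closure date was itself prompted by accumulating data, and the report should say so.

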2.1.2 Safety analysis set

The safety analysis set (SAF) will include all patients who received at least one dose of study treatment (regardless of whether that was the randomised therapy intended or indeed whether, in rare cases, they received therapy without being randomised), according to the study treatment they actually received, defined as below:

- if a patient received at least one dose of Olaparib, no dose of AZD6738 and no dose of AZD1775, then the patient will be counted for treatment arm 1 (Olaparib alone) in the SAF
- if a patient received at least one dose of AZD6738 and no dose of AZD1775, then the patient will be counted for treatment arm 2 (AZD6738 + Olaparib) in the SAF
- if a patient received at least one dose of AZD1775 and no dose of AZD6738, then the patient will be counted for treatment arm 3 (AZD1775 + Olaparib) in the SAF
- if a patient received at least one dose of AZD1775 and at least one dose of AZD6738, then it will be decided at the Blinded Data Review Meeting to which treatment arm the patient will be assigned for the safety analysis.

All safety data and drug exposure data will be summarised and analysed using the SAF.

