- l All patients must receive a 5-HT3 antagonist, ondansetron (Zofran) 8 mg PO or granisetron (Kytrel) 1 mg orally prior to each dose of AZD1775. Additional doses of 5-HT3 antagonist may be used if needed. In addition, dexamethasone 4 mg orally will be given with each AZD1775 dose as a minimum on the first day of dosing AZD1775 of every 3 days dosing period, unless contraindicated or not well-tolerated. Dexamethasone may be continued on further days of dosing, potentially at a lower dose. Dexamethasone or the 5-HT3 antagonist may be given by IV. Promethazine (Phenergan), prochlorperazine (Compazine), and benzodiazepine may still be used as additional adjunctive treatments during AZD1775 therapy. **Please note: aprepitant [E-mend] and fosaprepitant are not permitted due to known DDIs. No longer applicable following CSPv6.0, provided there has been a minimum washout period of 10 days since the final dose of AZD1775.** Patients should be strongly encouraged to maintain liberal oral fluid intake.

- m **CCI** sample should be taken at same visit as scan, if possible. If a **CCI** sample was taken at a scan visit not coinciding with the CxD1 visit a **CCI** sample at the CxD1 visit is not required
- n Scan visit may be tied in with CxD1 visit, using ± 7 d window, if appropriate
- o Unscheduled D8 and D15 visits with complete blood counts should be done from C3 onwards if Grade 3/4 neutropenia, G4 thrombocytopenia or a dose interruption due to haematological toxicity was experienced in a prior cycle. If no further events are experienced in the subsequent 3 consecutive cycles, then the Day 15 CBC visit can be stopped. **No longer applicable following CSPv6.0.**
- p The pharmacogenetic blood sample can be obtained either at the first treatment visit or after randomisation

* Please note that cycle length for AZD1775+olaparib treatment arm is 21 days.

** Please note that for patients on the AZD1775+olaparib treatment arm, the continuous olaparib dose will be 200 mg bd. After April 2019, all patients randomised to this treatment arm discontinued AZD1775 and were offered the opportunity to continue olaparib monotherapy at 300 mg bd on a 21-day cycle starting at the patient's next treatment cycle to ensure a minimum 10 day wash out period from AZD1775 to olaparib monotherapy 300 mg bd dosing to avoid DDI.

PBMC=peripheral blood mononuclear cell

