3.5.3 Dose intensity

Relative dose intensity (RDI) is the percentage of the actual dose delivered relative to the intended dose through to treatment discontinuation. For combination treatment arms, RDI will be calculated separately for each study drug.

RDI will be defined as $\text{RDI} = 100\% * d/D$, where

- d is the actual cumulative dose delivered up to the actual last day of dosing
- D is the intended cumulative dose up to the actual last day of dosing (D is the total dose that would be delivered, if there were no modification to dose or schedule).

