3.5.4 Adverse events

AEs will be collected throughout the study, from date of informed consent until 30 days after the last dose of study treatment. Any events in this period that occur after a patient has received further therapy for cancer (following discontinuation of study treatment) will be flagged in the data listings.

Adverse events will be defined as treatment emergent if they onset, or worsen (by investigator report of a change in intensity), during the study treatment period (defined from date of first dose of any study treatment to date of last dose of any study treatment) or safety follow-up period (30 days after last dose of study treatment).

The Medical Dictionary for Regulatory Activities (MedDRA) will be used to code the AEs. AEs will be graded according to the National Cancer Institute Common Terminology Criteria for AEs (CTCAE Version 4.03).

Other significant adverse events

During the evaluation of the AE data, an AstraZeneca medically qualified expert will review the list of AEs that were not reported as serious adverse events (SAEs) and 'Discontinuation of Investigational Product due to Adverse Events' (DAEs). Based on the expert's judgement, significant adverse events of particular clinical importance may, after consultation with the Global Patient Safety Physician, be considered other significant adverse events (OAEs) and reported as such in the CSR. A similar review of laboratory/vital signs/ECG data will be performed for identification of OAEs.

AEs of special interest

The following AEs of special interest (AESIs) have been identified by the patient safety team and included in the study protocol:

AESIs for Olaparib are myelodysplastic syndrome (MDS), acute myeloid leukaemia (AML), new primary malignancy (other than MDS/AML) and pneumonitis.

Other categories may be added as necessary or existing terms may be merged. An AstraZeneca medically qualified expert after consultation with the Global Patient Safety Physician has reviewed the AEs of interest and identified which higher-level terms and which preferred terms contribute to each AESI. Further reviews may take place prior to database lock (DBL) to ensure any further terms not already included are captured within the categories.

There are no AESIs for AZD1775 or AZD6738 which require additional data collection.

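### Safety tables for the AZD1775+olaparib arm pool events on the combination with events after the April 2019 switch to olaparib alone, and olaparib dose intensity runs across the dose change

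*SAP*

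**What the plan says.** **The switch.** In the arm as designed, "the continuous olaparib dose will be 200 mg bd" (Protocol section 4, Table 5 footnote). The same footnote adds: "After April 2019, all patients randomised to this treatment arm discontinued AZD1775 and were offered the opportunity to continue olaparib monotherapy at 300 mg bd". The switch takes effect at the next 21-day cycle, which leaves at least 10 days after the last AZD1775 dose.

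**Assignment.** SAP 2.1.2 assigns by treatment taken, and counts a patient in treatment arm 3 "if a patient received at least one dose of AZD1775 and no dose of AZD6738". It adds: "All safety data and drug exposure data will be summarised and analysed using the SAF". The rule applies to the whole patient and has no time component.

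**Adverse events.** In SAP 3.5.4 the treatment period is "defined from date of first dose of any study treatment to date of last dose of any study treatment", followed by 30 days of safety follow-up.

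**Exposure and RDI.** SAP 3.5.2 and 3.5.3 derive these separately for each drug. RDI is 100% × d/D, with d the dose delivered and D the dose intended up to the last day of dosing. SAP 3.5.3 explains that "D is the total dose that would be delivered, if there were no modification to dose or schedule".

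**Outputs.** SAP 4.1.2 provides three treatment columns. The list of tables, figures and listings has no post-switch column or table.

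**Where the switch is addressed.** SAP version 2.0 was issued to reflect the closure. It deals with the switch in the arm description (1.2.2), the FAS rule (2.1.1) and a disposition count (4.2.10.8), but in no safety, exposure or dose-intensity rule.

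**The concern.** The safety objective compares each combination with olaparib monotherapy. After the switch, an arm 3 patient is taking olaparib alone, at a dose different from the one given with AZD1775. Events in that period say little about the combination, yet they appear in its column. The same holds for the summaries built on a worst value (laboratory shifts, highest QTcF, worst ECOG), where one post-switch value can become the patient's arm 3 result.

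Protocol 1.2.2 gives increased toxicity and no suggestion of benefit as the reasons for closing the arm. Its safety profile is therefore one of the main things the study can still report about it. A reader of the study report should be able to tell which events belong to the combination.

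The olaparib RDI row has a related problem. A value above 100% does not describe tolerability, and it can hide earlier reductions or interruptions in the same patient.

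**Working it through.** The documents state no figure to reproduce here. The check traces the rules and then applies the SAP 3.5.3 formula.

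**1. Where a post-switch event goes.** The patient has taken AZD1775 and no AZD6738, so SAP 2.1.2 gives arm 3. The last dose of any study treatment is the last olaparib dose, so under SAP 3.5.4 the event is treatment-emergent. SAP 4.1.2 has only the arm 3 column to put it in.

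**2. Which rows run through the switch.** Because exposure is derived per drug, AZD1775 exposure ends with the last AZD1775 dose. Olaparib exposure and olaparib cycle counts continue.

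**3. Olaparib RDI for a fully compliant switcher.** Inputs: 200 mg bd = 400 mg/day before the switch; 300 mg bd = 600 mg/day after it; D held at 400 mg/day throughout. The durations are assumed: *a* days at 200 mg bd, then *b* days at 300 mg bd.

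RDI = 100% × (400a + 600b) / (400(a + b)) = 100% × (1 + 0.5 × b/(a + b))

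| a | b | b/(a + b) | Olaparib RDI |
|---|---|---|---|
| 126 | 21 | 0.143 | 107.1% |
| 126 | 42 | 0.250 | 112.5% |
| 126 | 84 | 0.400 | 120.0% |
| 63 | 84 | 0.571 | 128.6% |
| 63 | 168 | 0.727 | 136.4% |
| 21 | 168 | 0.889 | 144.4% |

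With D set separately for each period, the same patient has 100% in both.

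**4. AZD1775 RDI.** With the last day of dosing read as that drug's own last day, a compliant patient has 100%. If it were read as the last day of any drug, RDI would be a/(a + b), from 85.7% down to 11.1% in the rows above. The per-drug wording favours the first reading.

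**5. Direction of the effect on adverse events.** The AE tables count patients with at least one event. Added follow-up can only add patients. Let p be the incidence on the combination, f the share of patients who switch, and q the risk of a first event after the switch among those still event-free. The reported incidence is then p + f(1 − p)q. For illustration, with p = 30%:

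- f = 10%, q = 10%: 0.30 + 0.10 × 0.70 × 0.10 = 30.7%
- f = 40%, q = 20%: 0.30 + 0.40 × 0.70 × 0.20 = 35.6%

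The inputs p, f and q are all assumed, so this shows the mechanism and does not estimate the effect.

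**The case against.** Assigning the safety set by treatment received is conventional. Keeping every later event in arm 3 is also conservative, because delayed AZD1775 toxicity is not lost. That stands, and it rules out simply ending the main arm 3 window at the first monotherapy dose. Monotherapy may start 10 days after AZD1775, so such a cut could leave about 10 days of AZD1775 follow-up where the SAP otherwise allows 30, and crude arm 3 incidence would be biased downward against the comparator.

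The plan also separates some of this already. Related events, related events of grade 3 or higher, related serious events and discontinuations have tables specific to AZD6738 or AZD1775 (for example T 11.3.2.8, T 11.3.2.10, T 11.3.2.12 and T 11.3.4.3). This helps in part, since the relatedness tables rest on the investigator's attribution.

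For RDI, one can argue that 300 mg bd after the closure is the intended dose and not a modification, in which case nothing exceeds 100%. The SAP does not say so, and its definition of D points the other way. Protocol 6.8 also lets previously reduced patients step up gradually, so not every switcher would be on 300 mg bd at once.

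Four stronger readings are tempting but not supported:

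- *AZD1775's own exposure and RDI are distorted.* They are computed per drug and stop with AZD1775 on the natural reading.
- *Olaparib RDI would be reported as 150%.* That is 300/200 for the post-switch period alone. The planned RDI covers the whole course and so includes the days at 200 mg bd.
- *Post-switch time dilutes AE rates.* SAP 4.2.10.1 plans numbers and percentages of patients, not rates per person-time.
- *Incidence is inflated by ten points or more.* A reader might take 20 switchers among about 50 patients (350 − 2 × 3 × 50), six further months and a 5% monthly risk: 20 × (1 − 0.95^6) = 5.3 patients, or 10.6 points. None of the switching, duration or risk inputs is in the documents. The sum also assumes that every switcher is still event-free and that nobody stops treatment, although the plan's own assumed median PFS on olaparib is 5 to 6 months.

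**Conclusion.** The point holds as a gap in presentation. The SAP was revised for the closure, but its safety and exposure rules were not adapted to it. Arm 3 adverse-event incidence and worst-value summaries can therefore include findings on olaparib alone at a different dose. The direction for cumulative incidence is certain. The size is not computable, because neither the number of switchers nor their time on monotherapy is given.

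Olaparib exposure and cycle counts in arm 3 mix the two periods. Whole-course olaparib RDI exceeds 100% for a fully compliant switcher if D stays at the original dose, at about 107% to 144% for the assumed durations.

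The effect is confined to descriptive summaries of a closed arm. The ceralasertib versus olaparib comparison, for which the study is now sized, does not depend on it. This is an inexpensive improvement and does not threaten the trial's conclusions.

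**What to change.** - **Keep** the SAF and FAS rules and the pooled arm 3 safety tables.
- **Add** a supplementary presentation of arm 3 adverse events and worst-value safety summaries (laboratory, ECG, ECOG), limited to first dose through 30 days after the last AZD1775 dose. This reuses the SAP's existing follow-up length. Put later events on olaparib monotherapy in a separate column or listing.
- **In SAP 3.5.2 and 3.5.3**, report olaparib exposure and RDI in arm 3 separately for the combination and post-switch periods, with D defined as the intended dose of each period. State that the last day of dosing is drug-specific.

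The cost is one extra date cut and one extra column or listing, using dosing dates already collected. The restricted summary has shorter follow-up than the other arms. Because monotherapy may start 10 days after AZD1775, it can also contain up to 30 − 10 = 20 days of olaparib alone. Both limits belong in a footnote.
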